## 2. Definition of terms and abbreviations

The terms and abbreviations used in this statistical analysis plan are defined as follows.

Terms and abbreviations	Definition
Adverse events	An adverse event refers to any unfavorable and unintended sign (including an abnormal laboratory finding), symptom or disease associated with the use of a drug, whether or not considered related to the drug.
Adverse events during the safety analysis period	Adverse events that occurred during the period up to the start date of Humira treatment + 196 days.
Adverse events outside the safety analysis period	Adverse events that occurred prior to the start date of Humira treatment or after the start date of Humira treatment + 196 days.
Adverse reactions	Of adverse events, events for which causal relationship with Humira cannot be ruled out are defined as adverse reactions.
Adverse reactions during the safety analysis period	Of adverse events during safety analysis period, events for which a causal relationship with Humira cannot be ruled out are defined as adverse reactions during safety analysis period.
Adverse reactions outside the safety analysis period	Of adverse events outside safety analysis period, events for which a causal relationship with Humira cannot be ruled out are defined as adverse reactions outside the safety analysis period.
Basic statistics	Basic statistics include sample size, mean value, standard deviation, minimum value, median value, maximum value, first quartile and third quartile.
MedDRA/J	Medical Dictionary for Regulatory Activities/Japanese edition
SOC	MedDRA/J System Organ Class
PT	MedDRA/J Preferred Term
CDAI	Clinical Disease Activity Index
CRP	C-Reactive Protein
DAS	Disease Activity Score
DMARDs	Disease Modifying Antirheumatic Drugs
EULAR	European League Against Rheumatism
ESR	Erythrocyte Sedimentation Rate
JIA	Juvenile idiopathic arthritis
MTX	Methotrexate
NSAIDs	Non-Steroidal Anti-Inflammatory Drugs
SDAI	Simplified Disease Activity Index
VAS	Visual Analog Scale

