## 10. Data derivation and calculation methods

### 10.1. General

Name of data	Derivation and calculation methods
Age	Use the age shown in the CRF.
Number of investigating facilities	Aggregate the data for each facility code (DCF code).
Number of patients surveyed	Number of patients included in the safety analysis set.
Start date of Humira treatment	Of the start dates of treatment provided in “2. Status of Humira treatment”, the earliest date will be the start date of Humira treatment in each patient. (See “External file for provision of analysis”)
End date of Humira treatment	The latest date sorted by the end dates of treatment provided in “2. Status of Humira treatment” will be the end date of Humira treatment in each patient. (See “External file for provision of analysis”) In the case of ongoing patients, the date on which the final dosing was completed, which is provided in the CRF, will be the end date of Humira treatment. However, in patients whose end date of Humira treatment is “ongoing” or where the end date of Humira treatment calculated as above exceeds the start date of Humira treatment + 168 days, the end date of Humira treatment should be the start date of Humira treatment + 168 days.
Days to the date on which the last dosing of Humira was completed	End date of Humira treatment - Start date of Humira treatment + 1
Treatment status (total number of doses, total dose)	
 
• Total number of doses
 
 
(1) Data on “start date of treatment” and “number of doses” in “2. Status of Humira treatment” should be sorted in the order they are written.
 
(2) Dosing intervals should be calculated for each data on treatment status.
 
The intervals should be 14 days if “biweekly” is checked. If not, the intervals should be obtained from “External file for provision of analysis”.
 
(3) The number of doses should be calculated for each data on treatment status.
 
Number of doses = (end date of treatment [after complementation] - start date of treatment [after complementation])/dosing intervals (days)
 
*The end date of treatment in the last record should be the end date of Humira treatment.
 
(4) If the result of (3) is “>0” (greater than 0) and “<1” (smaller than

Name of data	Derivation and calculation methods

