	
1), it should be 1.
 
If “>=1” (1 or greater), the number should be rounded down to the nearest integer.
 
(5) The total number of doses should be the sum of (4) for each patient.
 
 
• Total dose
 
 
(1) If the dose of Humira is “other”, it should be obtained from “External file for provision of analysis”.
 
(2) Doses should be calculated for each data on treatment status.
 
Dose = number of doses x dose
 
(3) The total dose should be the sum of (2) for each patient.
 
 
• Mean dose
 
 
Mean dose = total dose / total number of doses

Discontinued patients	When the end date of Humira treatment is less than 24 weeks (168 days) after the start date of Humira treatment, the patient should be handled as a discontinued patient.
Reason for discontinuation	In the case of discontinued patients, data should be derived from “Reason for discontinuation” under “3. Discontinuation of treatment” of the CRF or “External file for provision of analysis”. If any data have not been provided, it should be handled as “unknown/unspecified”. “Onset of an adverse event” should apply only when “Onset of an adverse event” is selected and an adverse event during the safety analysis period has occurred.
Date of discontinuation of treatment	In the case of discontinued patients, the end date of Humira treatment should be the date of discontinuation. Where the start date of Humira treatment + 168 days > the end date of Humira treatment, the end date of Humira treatment should be the date of discontinuation.
Patients switched to other biological products	Patients falling under discontinued patients, for whom “Switching to another drug” is selected for “Treatment status after discontinuation” under “3. Discontinuation of treatment” of the CRF and whose “Drug name” falls under codes of biological products listed in “Drug code list 20171012.xlsx”.
Reason for switching	In the case of patients switched to other biological products, data should be derived from “Reason for discontinuation” under “3. Discontinuation of treatment” of the CRF or “External file for provision of analysis”. If any data have not been provided, it should be handled as “unknown/unspecified”. “Onset of an adverse event” should apply only when “Onset of an adverse event” is selected and an adverse event during the safety analysis period has occurred.

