Timing of onset of adverse events	
With the start date of treatment as Day 1
 
Adverse events that occurred after the start of treatment and within 4 weeks of treatment (Days 1 to 28)
 
Adverse events that occurred after Week 4 of treatment and within 8 weeks of treatment (Days 29 to 56)
 
Adverse events that occurred after Week 8 of treatment and within 12 weeks of treatment (Days 57 to 84)
 
Adverse events that occurred after Week 12 of treatment and within 16 weeks of treatment (Days 85 to 112)
 
Adverse events that occurred after Week 16 of treatment and within 20 weeks of treatment (Days 113 to 140)
 
Adverse events that occurred after Week 20 of treatment and within 24 weeks of treatment (Days 141 to 168)
 
Occurrence of adverse events after the end of treatment: Adverse events that occurred at and after Week 24 of treatment (on and after Day 169)

Adverse events occurred during treatment	Adverse events that occurred after the start date of Humira treatment by the end date or the date of discontinuation of Humira treatment
Adverse events occurred after treatment	Adverse events that occurred after the end date or the date of discontinuation of Humira treatment by the start date of Humira treatment + 196 days
Serious adverse events	Adverse events whose seriousness set through the AE matching activities is “serious” are defined as serious adverse events.
Adverse reactions	
Adverse events whose causal relationship is other than “not related” based on company-determined data set through the AE matching activities are defined as adverse reactions.
 
Adverse reactions with the same case number should be counted as one event when the PT is the same.
 
Name of analytical dataset: A_AE_AL
 
Names of variables: AERELS, AESOCCD, AEPTCD

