Purpose of analysis: The number and percentage of patients will be calculated for each implementation status (tested, not tested, unknown/unspecified) of hepatitis B test (HBs antigen test, HBs antibody test, HBc antibody test). Where tests were performed, the number and percentage of patients will also be calculated for breakdown of their results (negative, positive, unknown/unspecified).

Note: None in particular.

“Table 1.8 Status of Humira treatment (dosage and administration)”

Analysis object: Patients included in the safety analysis set

Purpose of analysis: For the status of Humira treatment (dosage and administration) (20 mg/2 weeks, 40 mg/2 weeks, 20 mg/2 weeks → 40 mg/2 weeks, other), the number and percentage of patients will be calculated.

Note: Patients who received doses other than “20 mg/2 weeks”, “40 mg/2 weeks”, “20 mg/2 weeks

→ 40 mg/2 weeks” should be categorized into “other”.

“Table 1.9 Status of Humira treatment (number of doses, days to the date of the last dosing)”

Analysis object: Patients included in the safety analysis set

Purpose of analysis: For the status of Humira treatment (number of doses, days to the date of the last dosing), the number and percentage of patients will be calculated by category defined in “11. Data-layer separation”.

Note: Where the last record of the treatment status is checked for “ongoing” or where the end date of treatment exceeds the start date of treatment + 168 days, the end date of treatment should be handled as the start date of treatment + 168 days.

“Table 1.10 Dose by body weight at the start of treatment”

Analysis object: Patients included in the safety analysis set

Purpose of analysis: The number and percentage of patients will be calculated for each category of dose at the start of Humira treatment as defined in “11. Data-layer separation” (number of doses, days to the date of the last dosing) by body weight at the start of Humira treatment (<15 kg, ≥15 kg and <30 kg, ≥30 kg, unknown/unspecified).

Note: The denominator of the percentage of the number of patients should be patients included in the safety analysis set.

“Table 1.11 Incidence rate of administration errors caused by self-injection”

Analysis object: Patients included in the safety analysis set

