#### “Table 2.15 Frequency of adverse reactions”

Analysis object: Patients included in the safety analysis set

Purpose of analysis: Adverse reactions during the safety analysis period will be aggregated in accordance with “11. Data-layer separation” (timing of onset of adverse events) as shown below. The number of patients analyzed, the number and

percentage of patients who experienced adverse reactions, the number of adverse reactions, the number of patients who experienced adverse reactions by type of adverse reaction (by SOC and PT) and their percentages against the patients analyzed will be calculated.

Number of patients analyzed: Number of patients receiving treatment by period.

Number of patients who experienced adverse reactions: Number of patients who experienced adverse reactions during the administration period. When a single patient experienced multiple episodes of the same adverse reaction (PT), the event that occurred at the earliest time should be counted as one case.

Number of adverse reactions: Number of adverse reactions that occurred during the administration period. When the same adverse reaction (PT) occurs multiple times in the same case, the event that occurred at the earliest time is counted as one case.

Types of adverse reactions: Should be calculated by SOC and by PT. Output data should be sorted in the order of international agreements and in the ascending PT code order. When the same adverse reaction (PT) occurs multiple times in the same case, the event that occurred at the earliest time is counted as one case.

Note: The version of MedDRA/J used should be provided.

“Table 2.16.1 List of adverse events that occurred during and after treatment”

Analysis object: Patients included in the safety analysis set

Purpose of analysis: Adverse events during the safety analysis period will be aggregated for the entire population, patients ongoingly treated at Week 24 of treatment, and discontinued patients (during treatment, after treatment, overall) as shown below.

During treatment: Adverse events that occurred after the start date of Humira treatment by the end date or the date of discontinuation of Humira treatment

After treatment: Adverse events that occurred after the end date or the date of discontinuation of Humira treatment by the start date of Humira treatment + 196 days

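### Capping the Humira end date at start + 168 days lets events in patients still on treatment be labelled as after treatment, and the SAP's two timing rules disagree on Day 169

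*SAP*

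**What the plan says.** - **End of treatment (SAP 10.1).** For patients recorded as ongoing, or whose derived end is later than the cap, "the end date of Humira treatment should be the start date of Humira treatment + 168 days". Table 1.9 (SAP 13.1) repeats the rule: "the end date of treatment should be handled as the start date of treatment + 168 days".
- **Discontinuation (SAP 10.1).** A patient counts as discontinued "When the end date of Humira treatment is less than 24 weeks (168 days) after the start date of Humira treatment". A capped patient does not meet this.
- **Safety period (SAP 2).** "Adverse events that occurred during the period up to the start date of Humira treatment + 196 days".
- **After-treatment events (SAP 10.2).** Those that "occurred after the end date or the date of discontinuation of Humira treatment by the start date of Humira treatment + 196 days".
- **Onset classes (SAP 10.2).** The start date is Day 1. The last class, from Day 169 onward, reads: "Occurrence of adverse events after the end of treatment: Adverse events that occurred at and after Week 24 of treatment".
- **Layers (SAP 11).** The top class for days to last dosing is for patients ongoing at day 169. The last onset class is named only by time, as after Week 24.
- **Tables 2.16.1 and 2.16.2 (SAP 13.2).** For Table 2.16.1, "Adverse events during the safety analysis period will be aggregated for the entire population, patients ongoingly treated at Week 24 of treatment", and then for discontinued patients, followed by a bracket listing during, after and overall. Table 2.16.2 has the same grouping for serious events.
- **Tables 2.14 and 2.15 (SAP 13.2).** These use the section 11 onset layers. The denominator is patients receiving treatment in each period, and reactions are counted during the administration period.
- **Protocol 6(3), 8(1) and 8(5).** Twenty-four weeks is the observation period. Malignancy is followed through the first and second years of treatment.

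**The concern.** The cap is reasonable for summarising exposure within the observation period. The same derived date, however, also decides whether an event falls during or after treatment, and the event window runs four weeks past the cap. A patient who is still injecting is thus treated as having stopped. I found no rule that goes back to the uncapped date to classify events.

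Events during or after the treatment period are an analysis item in Protocol 9(1), and SAP 3.1 says the results feed the report to the authority and the reexamination application. A reader of an after-treatment column will take its events as having occurred off drug. For some patients that could be false. At the 14-day interval in SAP 10.1, a patient on schedule has injections at 13 × 14 = +182 and 14 × 14 = +196 days. A site reaction to the +182 injection would meet the after-treatment definition, although administration site reaction is a priority survey item.

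**Working it through.** **Inputs.** Cap at +168 days (SAP 10.1); safety window to +196 days (SAP 2); start date = Day 1, last onset class from Day 169 (SAP 10.2).

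**The plan's own figure.** 24 weeks × 7 = 168 days, as stated in SAP 10.1. Likewise 28 × 7 = 196.

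**Scale.** Day number = offset from start + 1. So +168 is Day 169 and +196 is Day 197. The window from offset 0 to +196 holds 197 days.

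**How the SAP classes a capped patient.** Days to last dosing = end − start + 1 = 168 + 1 = 169, which puts the patient in the class ongoing at day 169. The end date is not less than 168 days after the start, so the patient is not discontinued.

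**Both timing rules, applied to a patient on Humira throughout the window:**

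| Rule | Labelled after treatment | Days | Share of window |
|---|---|---|---|
| End date (10.1 with 10.2) | offsets +169 to +196 (Days 170-197) | 196 − 168 = 28 | 28/197 = 14.2% |
| Onset class (10.2) | offsets +168 to +196 (Days 169-197) | 197 − 169 + 1 = 29 | 29/197 = 14.7% |

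The rules differ on one day. Offset +168 (Day 169) is during treatment by the end-date rule and after the end of treatment by the onset rule.

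**From patient to survey.** The documents do not give the proportion still on Humira at Week 24. Let it be *f*, and assume a constant event rate and a common 197-day window. The share of all events that are on-treatment but labelled after treatment is *f* × 28/197 or *f* × 29/197:

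| *f* (assumed) | End-date rule | Onset rule |
|---|---|---|
| 0.5 | 7.1% | 7.4% |
| 0.7 | 9.9% | 10.3% |
| 0.9 | 12.8% | 13.2% |
| 1.0 | 14.2% | 14.7% |

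**Denominator of the last onset class.** With capped dates, an ongoing patient is on treatment for one day of that class (Day 169) by the end-date rule, and for none of it if the class means after treatment. The number of patients receiving treatment in that period is therefore undefined.

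**The case against.** Four points limit the reach of the problem, and all stand at least in part.

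1. **Tables 2.16.1 and 2.16.2.** A reader might infer that on-drug events in completers are certain to move to an off-drug column. The during/after bracket directly follows the discontinued patients and may apply only to them. For them the recorded end date is used and the cap does no harm. Even on the wider reading, patients ongoing at Week 24 are a separate group, so the affected events can be found. The text does not settle which reading is meant, and the definitions in SAP 10.2 are not restricted to discontinued patients.
2. **Tables 2.14 and 2.15.** A reader might infer that these will carry the after-end-of-treatment label. They follow section 11, whose label is neutral. What remains is a conflict between sections 10.2 and 11, plus the unclear denominator.
3. **Early stoppers.** A reader might also infer the reverse error: someone who stops at Week 6 and reacts at Week 10 is shown in a week-of-treatment class. The restriction to the administration period and to patients receiving treatment may exclude that patient from both counts. The SAP is unclear here, not demonstrably wrong.
4. **Size.** The 14-15% is not an estimate of the survey's result. The CRF is completed after 24 weeks, so capture of general events from +169 to +196 days may be incomplete, although safety-information data are also matched in (SAP 10.2). In Tables 2.14 and 2.15, repeats of a preferred term count once, at the earliest onset. Both features push the late share down.

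**Conclusion.** The concern holds as a fault of attribution and labelling. As written, SAP 10.1 and 10.2 class events at +169 to +196 days as post-treatment in patients whom the SAP itself calls ongoing, and they contradict each other on Day 169. Whether this reaches Tables 2.16.1 and 2.16.2 depends on an ambiguous bracket.

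For an ongoing patient, 28 or 29 of 197 days are affected. The corresponding 14-15% of that patient's events assumes a constant event rate and full capture after Week 24, and is probably an upper bound. The survey-wide 7-15% further assumes that 50-100% of patients are ongoing. The documents give no figure for this, so they do not support calling completers the largest group.

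No event is lost: overall incidence, the priority-item table and the background-factor tables count all reactions to +196 days and are unaffected. Nor do the documents establish that every patient marked ongoing was in fact treated to +196 days, because the plan does not clearly collect dosing after Week 24.

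**What to change.** - Restrict the +168-day cap to exposure summaries such as Table 1.9.
- For the during/after split, use the recorded, uncapped end date. For patients marked ongoing, show events after +168 days in a separate column for events after Week 24 with treatment ongoing, not as after treatment. Alternatively, assume continued treatment, but only as a stated convention.
- Name the last onset class in section 10.2 by time since start (Day 169 onward, to start + 196 days), consistent with section 11, and give Day 169 the same status under both rules.
- State which groups in Tables 2.16.1 and 2.16.2 receive the during/after split.
- State which patients form the denominator of the last onset class in Tables 2.14 and 2.15, and how reactions after early discontinuation are placed.

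The cost is a handful of SAP definitions and table notes and a re-run of Tables 2.14 to 2.16.2. No new data are needed: recorded end dates and the ongoing flag are already inputs to SAP 10.1.

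### The SAP treats one Humira end date both as the last dosing date and as a date one interval later, so the during/after-treatment split for patients who stop is not fixed

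*SAP*

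**What the plan says.** SAP Section 10.1 gives two rules for the end date.

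- **General rule, which covers patients who stop:** "The latest date sorted by the end dates of treatment provided in" the CRF treatment-status section. What that CRF field records is not stated.
- **Ongoing patients:** "In the case of ongoing patients, the date on which the final dosing was completed" is used at first. It is then superseded, because for anyone ongoing or treated beyond that point "the end date of Humira treatment should be the start date of Humira treatment + 168 days".

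Four other definitions use this date.

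- **Time to last dosing.** The variable named "Days to the date on which the last dosing of Humira was completed" is computed as "End date of Humira treatment - Start date of Humira treatment + 1". Table 1.9 tabulates it as days to the last dosing.
- **Dose count.** For each treatment record, doses are (end − start)/dosing interval, with 14 days for biweekly use. Step (4) sets results between 0 and 1 to 1 and rounds results of 1 or more down.
- **Discontinuation date.** "In the case of discontinued patients, the end date of Humira treatment should be the date of discontinuation". There is no separate date for the decision to stop.
- **During and after treatment.** Section 10.2 runs *during* from after the start date up to the end or discontinuation date. It defines *after* as "Adverse events that occurred after the end date or the date of discontinuation of Humira treatment", up to start + 196 days. Tables 2.16.1 and 2.16.2 repeat this split, with an overall column.

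Protocol Section 9 (1) 2) lists adverse events during or after the treatment period as an item to be analyzed.

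**The concern.** Adalimumab is tabulated here as an injection with a 14-day interval. If the end date is the last injection, a patient who stops is treated as off drug from the next day. A reaction that begins some days after an injection, and leads to the next one being withheld, would be shown as post-treatment. Patients still on treatment are counted as *during* up to start + 168 days, wherever their last injection fell. Table 2.16.1 presents both groups, so part of any difference between them would come from the definition.

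The *after* column can also include time on a replacement biologic, since Section 10.1 identifies patients who switch. Mixing that time with the final Humira interval makes the column hard to interpret.

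There is also a boundary problem at the start. Read literally, events on the start date itself are in neither column. Yet the onset-timing rule in the same section makes the start date Day 1 and counts Days 1 to 28 as the first period. Administration site reactions are a priority survey item, so Day 1 matters.

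**Working it through.** **Inputs.** The interval is 14 days (SAP 10.1, biweekly), the cap is start + 168 days (10.1), and the safety period ends at start + 196 days (Section 2). The worked schedule is an assumption: k biweekly injections on days 0, 14, ..., 14(k − 1) after the start date.

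**The plan's own figure.** A patient carried to the cap has 168/14 = 12 doses, which matches the top Table 1.9 category (12 or more). The formula therefore works when the end date closes the twelfth interval.

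**Reading A: end date = last injection.** The quotient is 14(k − 1)/14 = k − 1.

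| Injections k | End date (start +) | Doses counted | Days to last dosing |
|---|---|---|---|
| 1 | 0 | 0 | 1 |
| 2 | 14 | 1 | 15 |
| 6 | 70 | 5 | 71 |
| 12 | 154 | 11 | 155 |

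The Table 1.9 label is right and the dose count is one short. A single injection gives exactly 0. Step (4) does not handle that value, the lowest Table 1.9 category (1 to under 2) does not hold it, and the mean dose becomes 0/0.

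**Reading B: end date = last injection + 14.** The quotient is 14k/14 = k, so the dose count is right. The label is then wrong: for k = 2, days to last dosing is 28 + 1 = 29 instead of 15. That moves the patient from the 1–28 to the 29–84 day category.

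**Between A and B.** If the date falls 1 to 13 days after the last injection, the count is still k − 1 for k of 2 or more. Only k = 1 is rescued, by step (4).

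The label and the dose count therefore cannot both be right for k of 2 or more.

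**Effect on the during/after split, Reading A.** Counting Day 1 as *during*, the window holds 14(k − 1) + 1 of the 14k days up to the next due injection:

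- k = 1: 1/14 = 7%
- k = 2: 15/28 = 54%
- k = 6: 71/84 = 85%

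The shortfall is always 14k − [14(k − 1) + 1] = 13 days. If the start date is excluded, as the wording literally says, the window for k = 1 is empty.

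**Example.** Three injections, the last at start + 28, then treatment stops:

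| Onset (start +) | Reading A | Reading B |
|---|---|---|
| 20, 28 | during | during |
| 29, 35, 41, 42 | after | during |
| 43 | after | after |

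**The case against.** The strongest reply is that nothing is shown to be misclassified. For patients who stop, the end date is a CRF end-of-treatment date whose definition is not in the documents, and the final-dosing wording of the end-date rule is confined to ongoing patients. The dose count makes sense only if a full interval is included, and on that reading the split is sound. This stands as far as it goes: that the end date *is* the last injection is an inference. It does not clear the plan, because the same section names a variable computed from that date as time to last dosing.

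Two further inferences are tempting but not supported.

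- **That the event prompting the stop always lands in the *after* column.** The *during* window includes the end date, so an onset on or before the last injection day, including a same-day injection reaction, is *during*.
- **That early discontinuation is overstated in Table 1.1.** A patient recorded as ongoing is set to start + 168 days and is not counted as discontinued. A patient whose last injection was at day 154 is counted only if treatment really stopped, and calling that discontinuation is a defensible convention.

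The consequences are also bounded. The split does not remove events from the overall column. The main ADR incidence tables run to start + 196 days regardless of it, and causality is assessed separately. Tables 2.14 and 2.15 are less certain, because their denominator is patients receiving treatment by period and may use the end date.

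On Day 1, the onset-timing rule suggests that inclusion was intended. The wording still needs correcting. Finally, the column list in Table 2.16.1 could be read as applying only to discontinued patients. In that case the unequal cut shows mainly within the stoppers' own columns.

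**Conclusion.** The inconsistency is established from the SAP alone: one date carries two meanings that cannot both hold. The misplacement of safety events is conditional. If the last-dosing label is taken at its word, all events with onset after a stopper's last injection go to *after treatment*, including those in the next 13 days, while ongoing patients are cut at start + 168 days. If the CRF date already includes the final interval, the split is acceptable and the fault lies in the Table 1.9 label.

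The percentages assume biweekly injections on schedule and treat the interval after an injection as exposed time. The SAP defines no such residual period. The number of stoppers, and of events in their final interval, is not in the documents. No test, sample size or main ADR incidence depends on this. It is a definition worth correcting before the tables are read, not a defect that undermines the survey's main results.

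**What to change.** **Section 10.1.** State what the end date is for patients who stop, and choose one of two consistent sets.

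- **Last injection date.** Keep the Table 1.9 label and add 1 to the rounded-down quotient for records that end on an injection date, so that k injections count as k and a single injection as 1. Patients set to start + 168 days keep 168/14 = 12, because that date is a cut-off and not an injection. Say whether earlier records, before a dose change, follow the same rule.
- **End of the final interval,** if that is what the CRF field records. Keep the dose count, relabel the Table 1.9 variable, and add no further interval anywhere. Adding 14 days in this case would count the interval twice.

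**Section 10.2 and Tables 2.16.1 and 2.16.2.** Define *during treatment* as the start date (inclusive) to the earlier of last injection date + the dosing interval already derived in 10.1 and start + 168 days. Define *after treatment* as the following day to start + 196 days. The 168-day cap keeps stoppers from being counted as *during* for longer than ongoing patients.

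**Leave the definition of discontinued patients unchanged.** Altering it would also change Tables 1.1, 1.2, 2.5.2 and 3.2.1.

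**Cost.** SAP edits and a rerun of Tables 1.9, 2.16.1 and 2.16.2 and the dose items of Table 4.4, plus a check of how the denominators of Tables 2.14 and 2.15 are derived. No new data are needed.
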